Our analysis (of the adherence outcome) will be a (censored) mixed effects linear regression model, also known as a mixed tobit model, to estimate the effect of the intervention versus SOC on logarithmically transformed levels of TFV in hair. Since large relative differences between very low hair levels are less clinically important than similar relative differences between higher levels, we will censor undetectable levels at the lower detection limit, and we will also add the detection limit to all levels before log-transformation. These steps reduce the influence of minor differences between levels at or near the detection limit, while preserving the approximate interpretation of back-transformed regression coefficients as fold-effects. The predictor variable for intervention will equal zero for everyone at the baseline (0-month) visit (where hair levels reflect prerandomization baseline) and then will change for those in the intervention arm to equal 1 at all subsequent visits. A random intercept term will account for within-person correlation across the multiple visits; time point will be included as a categorical variable to account for systematic changes over time. We incude the pre-intervention TFV hair levels in the tobit model Correlations between self-reported adherence and pill counts over 30 days and hair levels will also be calculated.

Analyses will be by intention-to-treat. PrEP tenofovir drug levels in hair will be compared between arms using repeated measures mixed effects tobit model with baseline hair TFV included as a baseline covariate. The hypothesis of statistically significantly higher TFV levels will be tested at the month 12 time point. PrEP discontinuation, defined as missing a refill, will be analyzed as a time-to-event outcome using Cox proportional hazards regression with the pre-intervention TFV hair levels as a baseline factor in the model. If PrEP is discontinued by the treating clinician for safety reasons (but not adherence reasons), follow-up thereafter will be censored. Adjusted analyses will be performed to control for potential confounders based on our prior work assessing correlates of PrEP use: demographics (e.g., age, educational level), sexual behaviors (e.g., condom use, outside partnerships), medical status (e.g., depression), and beliefs (e.g., risk perception, PrEP efficacy). Stata package "st" and "metobit" will be used for analyses.

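### Month-0 hair TFV is both an outcome row and a covariate in the same model, so the standard error is about 25% too small and the type I error is nearly tripled

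*Combined protocol and SAP*

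**What the plan says.** The analysis of the hair outcome is in section 6.4, under the long-term adherence metric. The first paragraph describes a mixed tobit model for log hair TFV. On treatment coding: "The predictor variable for intervention will equal zero for everyone at the baseline (0-month) visit", and it "then will change for those in the intervention arm to equal 1 at all subsequent visits". On correlation and time: "A random intercept term will account for within-person correlation across the multiple visits", and "time point will be included as a categorical variable". On low values: "we will censor undetectable levels at the lower detection limit".

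Near the end of that paragraph comes: "We incude the pre-intervention TFV hair levels in the tobit model". The next paragraph says the arms will be compared with a "repeated measures mixed effects tobit model with baseline hair TFV included as a baseline covariate", and adds: "The hypothesis of statistically significantly higher TFV levels will be tested at the month 12 time point".

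No sentence drops the month-0 row from the outcome when the covariate is used, and no type of standard error is given.

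**The concern.** Setting the treatment predictor to zero for everyone at month 0 has a purpose only if the month-0 level is one of the modelled outcomes. That is a sound constrained longitudinal model. Putting the same measurement on the right-hand side as well regresses the month-0 row on itself. One slope then has to serve a row where it should be 1 and four rows where it should be the within-person correlation.

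Hair TFV is the only one of the three primary outcomes in section 6.1 that is compared between randomised arms. If its interval and p-value are too optimistic, the pilot could report an adherence effect produced by the model and carry it into the larger trial that it is meant to inform.

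**Working it through.** **Inputs from the documents.** 50 per arm and SD of change 1.2 log units (section 6.3); hair at months 0, 3, 6, 9 and 12 (section 5.2); random intercept, categorical time, single step indicator (section 6.4).

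**Assumed, because the documents do not give them.** Within-person correlation ρ (0.3 to 0.7, exchangeable) and the share of undetectable levels.

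**The plan's own figure.** SE of a difference in change = 1.2 × √(2/50) = 0.24. With a two-sided 5% t-test on 98 df, a difference of 0.68 has 80.1% power and 0.79 has 90.3%; e^0.68 = 1.97 and e^0.79 = 2.20. Section 6.3 is reproduced.

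**By hand, no censoring, no true effect, ρ = 0.5.** Within-woman variance w = 1.2²/2 = 0.72. Variance of the month-0 level = 0.72/(1 − 0.5) = 1.44.

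1. *Baseline slope.* The covariate is constant within a woman, so the fitted slope averages over the five rows: g = (1 + 4ρ)/5 = 0.60. The follow-up rows need 0.50.
2. *Residual covariances.* Month 0 with a follow-up: (1 − g)(ρ − g) × 1.44 = 0.40 × (−0.10) × 1.44 = −0.0576. Two follow-ups: 0.36 + (ρ − g)² × 1.44 = 0.3744, where 0.36 = 0.5 × 0.5 × 1.44 is the correct between-woman variance given baseline.
3. *Fitted random-intercept variance.* Over 6 follow-up pairs and 4 month-0 pairs: b = (6 × 0.3744 − 4 × 0.0576)/10 = 0.2016, instead of 0.36. The residual variance stays at 0.72.
4. *Reported SE.* Let k = b/(w + 5b) = 0.2016/1.728 = 0.1167. Information = (100/4) × (4 − 16k)/w = 25 × 2.133/0.72 = 74.1, so SE = 0.116.
5. *True sampling SD.* The estimate is the arm difference in mean follow-up residual minus 4k/(4 − 16k) = 0.219 times the arm difference in month-0 residual. A chance month-0 imbalance, with variance 1.44 × 2/50 = 0.0576, enters with coefficient −0.10 − 0.219 × 0.40 = −0.1875. The rest has variance (0.36 + 0.72/4) × 2/50 = 0.0216. Total = 0.0216 + 0.1875² × 0.0576 = 0.0236, so SD = 0.154.
6. *Consequence.* SE/SD = 0.756. The test rejects when |Z| > 1.96 × 0.756 = 1.48, which has probability 13.8%. Interval coverage is 86.2%.

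With baseline as covariate only, both the reported SE and the true SD are √0.0216 = 0.147.

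The same formulae at other correlations:

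| ρ | Reported SE | True SD | Ratio | Type I error |
|---|---|---|---|---|
| 0.3 | 0.105 | 0.133 | 0.79 | 12.3% |
| 0.5 | 0.116 | 0.154 | 0.76 | 13.8% |
| 0.7 | 0.125 | 0.170 | 0.73 | 15.1% |

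**Simulation check under the null, ρ = 0.5.**

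| Model | Mean SE | Empirical SD | Rejection |
|---|---|---|---|
| Linear (2,000 trials): as written | 0.116 | 0.155 | 14.3% |
| Linear: month 0 as outcome row only | 0.146 | 0.151 | 5.8% |
| Linear: month 0 as covariate only | 0.147 | 0.151 | 5.4% |
| Tobit, 30% censored (2,404 trials): as written | 0.123 | 0.163 | 13.7% |
| Tobit: month 0 as outcome row only | 0.153 | 0.156 | 5.2% |
| Tobit: month 0 as covariate only | 0.153 | 0.159 | 5.7% |

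Other tobit settings for the model as written (ρ 0.3 to 0.7, 30 to 50% censored, 0 to 20% dropout) gave 12 to 14% rejection. Without censoring, ρ from 0.2 to 0.85 gave 13 to 17%, and ρ = 0.1 gave 11%.

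**If a separate month-12 treatment term were fitted, with baseline still used twice.** Under exchangeable correlation the SE is 5 to 16% too small and rejection is about 7 to 10%.

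**The case against.** **The double use is inferred.** The sentence in the first paragraph does not use the word covariate and could mean only that month 0 is a row. The second paragraph names the covariate but not the month-0 row. Read as two alternative models, each is calibrated, and the two give almost the same answer. This does not rescue the text. The sentence in the first paragraph refers to the tobit model just described, nothing says that two models are intended, and two models for a primary outcome with no stated choice would also need correcting.

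**The headline size is for the step indicator.** The hypothesis is to be tested at month 12, and a month-12 term would bring the inflation down to 1.4 to 2 times nominal. That is correct, but the step indicator is the only treatment term the plan defines, and the inflation does not vanish. Under serially decaying (AR(1)) correlation of 0.7, double use rejected about 19% with the step term and 16% with a month-12 term.

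**The estimate itself is little harmed, and robust standard errors largely cure the problem.** This stands. The sampling SD rises only about 2 to 7%, and participant-clustered robust standard errors brought rejection to 5 to 7% even with double use. The plan does not specify them.

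**Using month 0 as an outcome row is not a full remedy.** This also stands. Under AR(1) correlation that model with model-based standard errors rejected 9 to 11%, against 5 to 6% for covariate only. Robust standard errors brought an 11% case to about 7%.

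**It is a pilot.** Section 6.3 says statistical significance on hair is not the goal. That lowers the stakes of the p-value, but section 6.4 still sets a test, and an interval covering about 86% misleads any use of the estimate for planning.

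**Conclusion.** The concern holds: the hair model is wrong as written. With the plan's step indicator and model-based standard errors, the reported SE is about 25% too small. The type I error is about 14% instead of 5%, 2.7 times nominal in the tobit with 30% censored. Hand calculation and simulation agree.

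The size rests on an assumed exchangeable correlation and an assumed share of undetectable levels. Over correlations of 0.2 to 0.85 the conclusion does not change; at 0.1 the error is about 11%. With a separate month-12 term the error is about 7 to 10%. The fault lies in the interval and the p-value far more than in the point estimate.

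**What to change.** Use month-0 hair TFV once, and name the chosen model as the primary analysis in section 6.4.

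- **Preferred:** keep month 0 as an outcome row with arm coded 0 for everyone, and delete both statements that add baseline hair TFV to the model. Undetectable baseline levels are then handled as censored outcomes, like those at every other visit.
- **Alternative:** keep the covariate, restrict the outcome rows to months 3, 6, 9 and 12, and say how an undetectable baseline enters as a covariate.

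With either choice, specify participant-clustered robust standard errors. They matter most for the preferred option, which relies more on the random-intercept correlation being right. Also state whether the month-12 test uses the step coefficient or a separate month-12 term.

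The cost is a few sentences of SAP wording and no new data. The reported interval becomes wider: at ρ = 0.5 the SE goes from about 0.116 to about 0.147, which is the honest width.

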7. PARTICIPANT REIMBURSEMENT

Study participants will be reimbursed for time of visits, inconvenience of study procedures, and transport expenses. The reimbursement per screening or follow-up visit will be 200 Kenyan Shillings (KSh). The reimbursement will be collected after the participant has completed their study visit. The participants will be told, "You will receive a transportation reimbursement and an additional 200 Kenyan shillings for your time and effort."

8. SAFETY

8.1. Risks to Human Subjects

Multinational studies, including the Thika site, which conducted Partners PrEP Study and Partners Demonstration Project demonstrated that PrEP (including FTC/TDF) was safe for use in heterosexual men and women from Kenya and Uganda. There were no statistically significant differences in the frequency of deaths, serious adverse events, adverse events overall, or key laboratory adverse events (specifically, creatinine elevation and phosphorus decrease) for those receiving PrEP compared to those receiving placebo in the Partners PrEP study.

For the purposes of this study, only serious adverse events (SAEs), and adverse events felt related to PrEP adherence testing will be documented. SAEs felt to be related to PrEP will result in temporary hold of PrEP. In the case of temporary holds, the hold will continue until the event is stabilized or resolved. If the event resolves, PrEP may be reinitiated at the discretion of the Investigator, resuming safety monitoring. The severity of clinical symptoms will be scored using the DAIDS Table (July 2017 2.1 Version; https://rsc.niaid.nih.gov/clinical-research-sites/daids-adverse-event-grading-tables) for Grading the Severity of Adult and Pediatric AEs. Reporting on adverse events to the medical officer and relevant IRBs will be according to relevant regulations. Moreover, the study will be alert to any unanticipated problems which might arise in the conduct of the study (e.g. social harms) and take steps to minimize such problems (as detailed in Section 8.2). If any unanticipated problems arise, these will be reported to the relevant IRBs (KEMRI and UCSF) immediately.

Participants may feel pain or discomfort from phlebotomy if selected for a blood sample archive. Participants may become embarrassed, worried, or anxious when answering behavioral or demographic questions. We have trained counselors who are available through the study to help participants deal with any feelings or questions they may have. The study staff will make every effort to protect participant privacy and confidentiality while in the study. However, it is possible that participants' involvement in the study could become known to others, and that social harms may result (i.e., because participants could become known as participating in a trial involving those at risk of HIV). For example, participants could be treated unfairly or discriminated against, or could have problems being accepted by their families and/or communities.

8.2. Adequacy of Protection Against Risks

Recruitment and Informed Consent

The study protocol, consent forms, and project materials have been reviewed and approved by KEMRI Scientific and Research Unit (SERU) in Kenya (KEMRI IRB approval in **Appendix IX**). All consent forms and participant education materials will be available in English and Swahili, as appropriate. In developing the Swahili consent form, the English document will be translated into Swahili, and a separate person will back-translate the document into English. This process of back-translation of the Swahili consent form will help ensure a satisfactory translation. Throughout the recruitment and informed consent process, we will adhere to ethical norms that are standard to the study setting.

During the course of the study, confidentiality will be preserved and the data will be maintained in a secure cabinet in the research office. The logbook containing the study identification numbers, completed consent forms, and completed data forms will remain on the premises and stored in a locked cabinet. The online data will be stored in REDCap, which is a password protected data management service. All computers with access to the data will be password protected. All data will be analyzed using the participants' study identification number and not their identifiable information.

Protection Against Risk

We will take several steps to minimize risks for participating in the proposed research project. First, the research assistant will emphasize the voluntary nature of study participation and that participants are free to withdraw from the study at any time and without impact to their routine medical care. At any point during interviews, participants (women taking PrEP and healthcare providers) can decide to not answer any question they are uncomfortable answering and may choose to leave the interview or focus group sessions at any time. Second, the study protocol, consent forms, and project materials will be reviewed and approved by the Institutional Review Board in Kenya prior to commencing the study or recruiting participants. Ethical review boards have a Federal-Wide Assurance number. In addition, the consent forms will be translated to Swahili and then back translated into English to ensure accuracy. Third, we intend to minimize any potential breach of confidentiality by conducting interviews in a private space, maintaining study data in a locked office, entering data onto a secure website, and ensuring that all research computers are password protected.

We will take several steps to minimize the clinical risks in the proposed research project. First, to minimize risks of discomfort, bleeding, and infection during the blood draws, we will always use sterile needles and syringes, practicing good technique, and conducting the procedures in a designated space. Second, to mitigate the risks of anxiety related to care and treatment related to HIV risk, we will be able to refer participants to accessible counselors and social workers.

Of note, the study team has extensive experience with counseling about HIV-1 risk and HIV-1 serodiscordancy, PrEP (and ART), and strategies for HIV-1 prevention in general. The risks from the anticipated activities will be no greater than in our previous studies; in fact, given the proven prevention benefits of PrEP and now national roll-out in Kenya, risks are anticipated to be less than in some of our prior studies. We feel the risks associated with the study are small. The benefits are consistent with clinical care benefits and cultural expectations and they follow the established standard with IRB approval in our other studies. We therefore believe the balance of benefit and risk is appropriate

Participants will be asked to inform the clinic staff if they feel they have been injured because of taking part in the study. Injuries may also be identified during laboratory testing, medical histories, and physical examinations. Treatment for adverse events related to study participation will be provided by the treatment clinic. If treatment is required that is beyond the capacity of the clinic, the clinic staff will refer the participant to appropriate services or organizations that can provide care for the injury.

8.3. Potential Benefits of the Proposed Research

Participants will be receiving PrEP as part of the standard of care. Potential benefits to the proposed research include allowing the participant to voice their opinion about the acceptability of this novel point-of-care test. Participants may feel useful to in helping researchers learn potentially new ways to measure and improve adherence to PrEP. Participants and others also may benefit in the future from information learned from this study on this novel urine-based adherence assay. There may be no other direct benefits to participants in this study

8.4. Ensuring patient confidentiality and safety

We will have several mechanisms in place to ensure participant confidentiality and safety. First, we will provide extensive training to the research team regarding the study protocol, consent form, the importance of maintaining participant confidentiality and safety. Laboratory technologists onsite at Thika responsible for interepreting the tenofovir urine assay will be extensively trained. Second, we will be in regular communication with the Thika clinic to ensure that we are not disrupting patient flow or treatment. Third, we will review our data on a regular basis to make certain that our proposed research projects are not causing harm or adverse events. The Principal Investigator will notify the Institutional Review Boards of any breaches in confidentiality, study protocol, or adverse events attributable to this study within ten days of the event. An Independent Study Monitor will review procedures for the study every 3 months with full details provided in Section 12.

8.5. Pregnancy among HIV-negative women

Animal and human date, including from the Partners PrEP Study and Partners Demonstration

Project, suggest safety of FTC/TDF when used by HIV-1 infected women during pregnancy and breastfeeding.{Joseph Davey, 2020 #1219}. For this study, PrEP will not be discontinued when pregnancy is detected. Moreover, per the 2016 Kenya PrEP treatment guidelines, urine pregnancy testing of all women of reproductive age will be conducted at the start of PrEP and when indicated for clinical care (**Table 1**, footnote).

8.6. HIV testing

HIV-1 testing is an essential component of PrEP delivery to protect patient safety – specifically, to prevent the initiation of PrEP among persons who have already acquired HIV-1 and to prevent continuation of PrEP if HIV-1 is acquired while receiving PrEP. In clinical trials and delivery projects of PrEP, the greatest risk of HIV-1 infection is at the time of initiation – either because of unrecognized chronic HIV-1 infection prior to HIV-1 testing as part of PrEP start or recent (acute) HIV-1 infection acquired just prior to PrEP initiation. Such testing will be routine in this study at PrEP initiation and at each PrEP visit (**Table 1**) according to the 2016 Kenya PrEP guidelines. Kenya recommends testing according to the national HIV-1 testing algorithm, which uses third-generation HIV-1 antibody based tests, done in sequence (i.e., if a positive first test, then perform a second test for confirmation, and a third as tie-breaker).

8.7. Social harm considerations for PrEP and PrEP adherence testing

PrEP use at this point is considered one of the most effective biomedical prevention interventions for HIV risk and the benefits far outweigth the risk, which is why PrEP is part of standard clinical guidelines in Kenya and around the world. For this study, we have considered the risk of the adherence counseling provided by the urine-based test. The formative work we are performing now to ask women about how they would like the test information delivered in a supportive, motivating manner (**Section 5.5**) based on how counseling was delivered in HPTN-082 (**Figure 8**) is vital to minimizing any risk of social harm from delivering the information. Moreover, the very low risk of misclassification of test results due to the urine assay's high performance characteristics (low risk of false positives or false positives) is also helpful to minimizing any risk (please see **Section 3.4**).

The 24-hour helpline that Thika clinic has, and which we have used for prior studies, will be available in case of anxiety, social harm, depression, or a positive HIV test. In the event of a clinical need (e.g., side effects, anxiety, symptoms of a sexually transmitted infection), participants will be requested to return to the clinic for care.

9. TIMELINE

The Study Aims will be completed in two years from the initiation of the study, according to the timeline detailed in **Table 2**.

1274

	Year 1		Year 2					
	Q1	Q2	Q3	Q4	Q1	Q2	Q3	Q4
RCT of PrEP Adherence								
IRB approval, Training & Preparation	X							
Enrollment Period		X	X					
Follow-up Period			X	X	X	X		
Laboratory Testing					X	X	X	
Qualitative Acceptability/Feasibility studies								
Data collection					X	X		
Data analyses and manuscripts						X	X	Х

12751276

1277

1278

1279

1280

1281

1282

1283

1284

1285

1286

1287

1288

1289

1290

1291

1292

10. LIMITATIONS

Urine levels, like those in plasma, represent short-term PrEP adherence. Therefore, adherence monitoring via these matrices may be susceptible to "white coat adherence", where adherence improves transiently before a clinic or a study visit. 130. We have designed this study to capture information on both short-term adherence (via the urine assay) and long-term adherence (via the hair assay) to evaluate for white-coat adherence patterns. 35,39,41 For instance, positive urine TFV assays but low concentrations of TFV in hair are suggestive of white-coat adherence patterns where short-term adherence is high, but long-term adherence is low. In intervention arm participants, short-term adherence may improve with feedback from the assay, but hair concentrations do not reflect "white coat" adherence and will only increase if overall adherence over time increases. Therefore, the careful design of the study and including both short-term and long-term adherence patterns will help us evaluate whether white-coat adherence is observed. Of note, we have elected to collect and store urine samples in the standard-of-care arm participants as well in order to analyze TFV detection at the end of the study in these samples. Hair levels will also be analyzed at the end of the study in SOC arm participants. This will enable us to compare whether the intervention arm participants (who knew urine tenofovir testing would be performed and the information delivered to them) had higher rates of "white coat adherence" than those in the standard-of-care arm.

129312941295

1296

12971298

1299

Another limitation is that we focus only on daily PrEP in this study. Intermittent PrEP has efficacy among MSM, ^{199,200} although there is no evidence for on-demand PrEP with heterosexual risk in men and in women. Updated CDC guidelines for MSM still recommend daily use. ²⁰¹ World Health Organization guidelines endorse daily use. Therefore, this study has relevance to the way in which PrEP should be administered in women worldwide.

Finally, the extensive validation data we have now published and summarize in **Section 3.3** shows the high performance characteristics of the assay. Our work evaluating the assay's performance in diverse populations using stored urine samples (e.g. Partners PrEP, manuscript in preparation) verifies its utility across real-world settings. We do not have specific information on the effect of concomitant medications on its performance (e.g. anti-TB drugs), although these are not expected to significantly affect the results of a yes/no tenofovir adherence assay.

1307 1308 1309

1310

1311

1312

1313

1314

1315

1316

1317

1318

1301

1302

1303

1304

1305

1306

